### **Procedures for SA3**

Initiation of Therapy: Within 6 months of the home monitoring identify OSA, subjects will return to the clinic for CPAP therapy and will undergo mask fitting and desensitization and CPAP education during this visit. CPAP education will follow a written protocol common to both sites. During the first two weeks of therapy, the research co-coordinator will call the patients each week to discuss any mask or CPAP related issues. If the subject experiences any problems, he/she may

return to the clinic for additional support or mask replacement. If more than 6 months elapse after the home monitoring and the subject wishes to participate in the CPAP trial, the subject will be asked to repeat the initial assessment including questionnaires, rhinomanometry, nasal lavage, and home sleep testing.

Randomization and Blinding: OSA patients will be randomly allocated to CPAP or CPAPFlex stratified by site and low ( $\log[\text{Reff}] \leq 1.0$ ) and high ( $\log[\text{Reff}] > 1.0$ ) resistance by the statistician. This will be accomplished by generating an allocation table of randomly permuted blocks of assignments to study condition (CPAP vs CPAPFlex) for each site. Outcome of the randomized choice of treatment will be provided to an unblinded individual (one at each site) who is not part of the analysis of the study data, and who will set the allocated CPAP device at the start of each treatment period. Devices will be tracked by serial number. Although subjects will be blinded to the therapy type, they may be able to perceive a difference in the mask pressure during expiration. CPAP and CPAPFlex machines are identical otherwise and no feedback will be provided to subjects regarding the type of treatment. The unblinded individual (not the PI) will maintain a master file containing numbered sealed envelopes containing the serial number, patient ID and designation code for each treatment period and subject. Except in an emergency situation these envelopes will not be opened until the study has been completed and all data have been entered/cleaned. The unblinded individual will document any premature unblinding that may occur. All data review relevant to adherence/titration scoring will be presented to the scorer as a flow signal alone, keeping the pressure data unvisualized so as not to reveal the presence of CPAPFlex. The automated report will indicate if there are significant deviations from prescribed pressure.

Monitoring of CPAP Efficacy and Adherence: Efficacy will be evaluated by (i) reviewing residual AHI and inspiratory flow limitation at optimal pressure as recorded on the device and (ii) review of raw airflow signal. Nightly adherence at the optimal pressure is recorded on the device and also transmitted to the sleep center.

Cross over to alternate therapy: Four weeks after the first intervention (ie CPAP or CPAPFlex), the device will be switched to the alternate mode by remote modem connection. The switch will take place after the subject has completed the telephone satisfaction questionnaire.

Subjective Assessment: At the end of each intervention period subjects will fill out ESS, Functional Outcomes of Sleep Questionnaire (FOSQ) and a satisfaction questionnaire. At the second clinic visit (for the CPAP training and mask fitting), subjects will be given two stamped envelopes, addressed to the research coordinator. The envelopes will each contain one copy of the ESS and FOSQ. After approximately 3 weeks of the first therapy mode, the subject will be called by a member of the study team. The investigator will interview the subject to complete the satisfaction questionnaire by phone. The satisfaction questionnaire must be completed prior to the switch to the alternate treatment period. The investigator will also remind the subject to complete the ESS and FOSQ and return it by mail. This will be repeated for the second therapy mode. The satisfaction questionnaire must be completed to conclude the CPAP trial. At the end of each the end of each treatment period, a study investigator will attempt to reach the subject at least 3 times to complete the satisfaction questionnaire. If the subject cannot be contacted, a letter will be sent requesting the subject to contact the investigator. During this contact period, the treatment period will be extended. If the subject does not respond within two weeks, he/she will be considered lost to follow-up.

### **3.5.1 Inclusion Criteria**

Subjects identified as new onset snoring (pre-post-9/11 score of  $\leq 2$  to 3-4) or non-snorer (score of  $\leq 2$  to  $\leq 2$ )

### **3.5.2 Exclusion Criteria**

(i) Gross skeletal alterations affecting the upper airway (eg. micrognathia) (ii) Unstable chronic medical conditions known to affect OSA (CHF, stroke) (iii) Pregnancy or intent to become pregnant within the period of the protocol (iv) Inability to sign informed consent form (v) habitual snorer or diagnosis of OSA prior to 9/11/01 (pre-9/11 score of 3-4) (vi) a perforated septum (vii) treatment for sleep apnea including surgery, current (within the past 2 months) use of a mandibular advancement device, or current (within the past 2 months) use of CPAP (viii) First WTCHP monitoring visit after 2/1/13 (viii) if the V1 questionnaire regarding snoring prior to September 11, 2001 is unavailable, the patient will be asked if he/she currently snores. Patients with no V1 snoring questionnaire who currently snore will be excluded.

### **3.5.3 Subject Recruitment**

Two recruitment methods for the WTCHP responders at Rutgers Robert Wood Johnson Medical School (RWJMS) may be used for the study.

#### **Clinic recruitment**

The primary recruitment for the WTCHP responders at Rutgers RWJMS will be in-person during a clinic visit. Prior to each appointment, the WTCHP staff mail appointment packets to responders. The packets contain a letter confirming their appointment, a copy of the WTCHP consent, and approved at-home questionnaires. As part of this mailing packet, a pre-visit flyer (Pre-Visit Study Announcement) announcing the study will be included. As WTC responders return to the clinic for an annual monitoring or treatment exam, the clinic staff will check the medical chart for eligibility. A member of the clinic staff will confirm that the patient has agreed to be contacted for future studies and that the subject had not reported habitual snoring (snoring several nights a week) prior to 9/11. A study flyer will be placed in the file. If the patient appears to be eligible, a nurse or physician will inform the patient about the study, give the patient a copy of the approved flyer and ask if they are interested. If the patient is interested in participating, they will be asked to provide their name, email/street address, and phone number on a postcard so that a member of the research team can speak with him/her about the research study. A box labeled with the study name will be placed in the waiting room to collect postcards from interested patients. The box is under observation by clinic staff and will be emptied by the research staff each day. If the patient cannot be reached by phone and did provide their street address, a follow up letter will be mailed to them. The letter will ask the patient to contact the research staff if he/she is still interested in the study. If the email address was provided, an approved email will be sent asking the subject to contact the research staff.

Interested patients will also be given the option of speaking with a study investigator during the clinic visit. The study investigator (the research coordinator/assistant) will meet with him/her in a private area to inform the potential subject about the study and go through the screening script. In addition, flyers and postcards will be placed in the clinic waiting room. Information about the study will also be posted on the EOHSI website (<http://eohsi.rutgers.edu/content/research-volunteers>).

### **Mail recruitment**

If the recruitment rate of WTCHP responders at Rutgers RWJMS via clinic visit is insufficient to meet recruitment goals, names of WTCHP responders at Rutgers RWJMS (the same study population) will be recruited by mail. Under WTCHP guidelines, for any mailing, names of responders at Rutgers RWJMS must be obtained from the Data Coordinating Center (DCC) for the WTCHP. Once the DCC has mailed the names to [name], the medical records will be checked to select responders who did not report habitual snoring prior to 9/11/01. The responders who did not snore will be sent a letter from [name], the principal investigator and medical director of the Rutgers RWJMS Clinical Center of the WTCHP. The letter will give the responders information about the study and let them know that they will be called by one of the study investigators. The letter will be followed by a phone call within a few weeks. This will give the responder some time to consider the study prior to being called by the study investigator.

To supplement the two recruitment methods, information about the study will be posted on the EOHSI website (<http://eohsi.rutgers.edu/content/research-volunteers>).

### **3.5.4 Consent Procedures**

**Clinic Recruitment:** If the subject has asked to be contacted about the study (placed a contact card in the clinic box), a study investigator (research assistant, research coordinator) will call the subject and read the study screening script for clinic contacts.

**Mail Recruitment:** If the subject has been recruited by mailing, a member of the clinic staff will call the subject and read the study screening script for DCC contacts.

After reading the script (either for clinic contacts or DCC contacts), if the subject is interested in participating, their contact information will be recorded, a copy of the consent form will be mailed, and an appointment will be made for the first clinic visit. The subject will be called the preceding workday to confirm the appointment. The subject will be asked if he/she is experiencing seasonal allergies or had a recent cold. If yes, the appointment will be re-scheduled so that all symptoms have subsided at least 2 weeks prior to the appointment.

**Clinic contacts only:** If the subject is in the clinic and requests information about the study, the screening may be done in-person, in a private office. If eligible, the subject will be given a consent form to read. After reading it, the investigator will review the study and answer any questions. The consent form will be signed by the subject and the investigator. The subject will be given a copy of the signed document. An appointment will be made for the clinical visit.

If the subject wishes to think about participating, he/she will be given a copy of the consent form to take home. The investigator will record contact information and contact the subject in a few days. If the subject wishes to participate, an appointment will be made for the clinic visit. Consent will be obtained on the day of the clinic visit as outlined below.

### **Consent Signature**

**Clinic and DCC contacts:** Subjects may return the signed consent form by mail. Once the consent form is received, an investigator will call the subject, answer any questions, and confirm participation. These subjects may then do the home sleep monitoring prior to their first clinic visit.

The monitor will be mailed with a signed copy of the consent form. If the clinic visit is scheduled first, on the day of the clinic visit, the consent form will be reviewed with the subject by a member of the study team. All questions will be answered. If the subject wishes to enroll, he/she will be asked to sign and date the consent form. The study investigator will also sign and date the consent form. The subject will be given a copy of the signed document.

### ***3.5.5 Subject Costs and Compensation***

After the completion of the clinic visit and the ARES home monitoring, subjects will be provided payment of \$100 dollars as compensation for their time. Subjects who have been diagnosed with sleep apnea and placed on CPAP will be allowed to keep the machine after completion of the study, if desired. Subjects will have an opportunity to refuse to participate at any time during the study.

## **4. Study Variables**

### ***4.1 Independent Variables or Interventions***

Both CPAP and CPAPFlex are standard treatments for sleep apnea. This study will test the efficacy of each treatment based on independent measures of nasal resistance.

### ***4.2 Dependent Variables or Outcome Measures***

Evaluation of sleep apnea will be based on sleep study performed in the home.

### ***4.3 Risk of Harm***

The physical risks to the study are minimal. All procedures are non-invasive and often performed in clinical settings.

Participants may experience slight discomfort from the pressure of the strap of the ARES monitor. The strap may be loosened. Additionally, in rare cases (<0.5%), participants have had a mild skin allergy to the synthetic fabric on the strap. The participants will be instructed to discontinue use of the monitor if any skin reaction is suspected. Some participants may be concerned about the diagnosis of sleep apnea. These subjects will discuss the diagnosis with the study physician and receive treatment with CPAP. Some people find CPAP uncomfortable. The subject may choose to continue or discontinue the use of CPAP. The other risk of the study is the disclosure of PHI. Every effort will be made to keep all PHI confidential.

### ***4.4 Potential for Benefit***

Patients with OSA will receive treatment. They will have an opportunity to evaluate two modes of treatment with CPAP (CPAP and CPAPFlex) and select the most comfortable mode. Subjects diagnosed with OSA will be allowed to keep their CPAP machines following the study period, unless they specifically indicate that they do not wish to use it, in which case the devices will be returned to the sleep laboratory.

Normal subjects will not benefit directly from participation in this study. However, the data from the study will provide new knowledge about conditions common to WTC exposed individuals.

Obstructive Sleep Apnea in WTC responders: Role of nasal Pathology

[name]

Evaluation of standard therapies in this population will help provide guidelines to physicians caring for these patients.

[Redacted text block]

[Redacted text block]

## **6. Data and Safety Monitoring**

All procedures in the study are minimal risk. Both CPAP and CPAPFlex have equal efficacy for the treatment of OSA. The PI will monitor this study for all patient safety issues. The PIs, [name] along with [name] (MSSM), will review these data as soon as they are available on each subject. Subjects will be given an access number to call during the work day during the study. Aggregate data reviews will be conducted annually at a minimum, and presented for review by the Rutgers-RWJMS, MSSM IRB and NYU IRB.

## **7. Reporting Results**

### ***7.1 Individual Results***

All patients will be given the results of their overnight sleep monitoring. Those diagnosed with OSA will be asked to meet with the study physician to review the results and discuss the diagnosis and treatment options. At the end of the study, those subjects who participated in the CPAP evaluation will be given a report documenting the appropriate titration for treatment and recommendations for follow-up. Subjects will also be asked if they wish to share the study results with the WTCHP clinic. If so, the subjects will be asked to sign an authorization allowing the study staff to release the records to the WTCHP clinic. No release of study information will be made without a written authorization.

### ***7.2 Aggregate Results***

Subjects will be given the option to receive a summary of the study results. Additionally, the summary results will be available on [ClinicalTrials.gov](http://ClinicalTrials.gov).

### ***7.3 Professional Reporting***

Results of the study will be published in peer-reviewed journals and may be presented at professional meetings. A description of this clinical trial will be available on [ClinicalTrials.gov](http://ClinicalTrials.gov), as required by U.S. Law.

## Primary Outcome Measure: Measure Title Adherence to CPAP

Measure Description: The use (number of hours per night) will be compared between standard CPAP and CPAP flex.

Statistical method:

Generalized estimating equations (GEE) models, with mean hours per night as the dependent variable, will be used to compare the device use of standard CPAP and CPAP flex.

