
**SA3. Relate nasal resistance to CPAP adherence in patients with OSA and show that reduction of expiratory pressure using CPAPFlex will improve CPAP adherence.** Patients with OSA will be randomized in a double blind cross over design to receive CPAP or CPAPFlex and adherence will be measured.

*In patients with OSA, we will test:*

*Hypothesis 3a: Increased nasal resistance is associated with decreased adherence to CPAP.*

*Hypothesis 3b: Use of CPAPFlex will improve adherence with CPAP in subjects with high nasal resistance, but not in those with low nasal resistance.*

*Hypothesis 3c: The benefit of CPAPFlex on adherence will be greatest if it is offered at CPAP initiation rather than as a “rescue” therapy in subjects with high nasal resistance.*

[figure not shown]

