CPAP keeps the UA open and nasal resistance becomes the primary determinant of total UA resistance. Thus, during CPAP use, high nasal resistance may continue to cause a patient to experience discomfort while exhaling despite adequate relief of OSA and could contribute to intolerance of CPAP. In preliminary data we have shown that, as expected, increased nasal resistance results in higher expiratory pressure. By decreasing this excess pressure during the expiratory cycle, CPAPFlex (Philips Respironics) may improve CPAP adherence. Although prospective, randomized studies have demonstrated that CPAPFlex is not inferior to conventional fixed CPAP, increased adherence has not been uniformly demonstrated. Some studies have shown CPAPFlex reduces discomfort and improves adherence, but larger randomized studies have shown no difference in adherence between CPAP and CPAPFlex. However none of these studies have attempted to target therapy to patients based on elevated nasal resistance as we propose to do. **In specific aim 3 of this proposal we will relate nasal resistance to CPAP adherence in patients with OSA and show that reduction of expiratory pressure using CPAPFlex will improve CPAP adherence.**

[Redacted]

[Redacted]

[Redacted]

[Redacted]

[Redacted]

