Home monitoring for OSA: Subjects will be given an ARES™ Unicorder (pictured) or a similar device (such as Embletta) and a separate wrist pulse oximeter (Nonin WristOx2 Model 3150) to take home and wear for 2 nights, with a pre-addressed mailer to return the devices to the sleep lab. The ARES Unicorder is routinely used in clinical practice for home monitoring of OSA. The ARES Unicorder is worn on the forehead and does not require additional wires to external devices. It measures oxygen saturation and pulse rate from reflectance oximetry, airflow from a nasal cannula/pressure transducer, snoring via acoustic microphone and head movement actigraphy and head position from accelerometers. The device also provides audible alerts during the study if poor quality airflow or SpO2 is detected so the subject can reposition the device. The wrist pulse oximeter

will be used to correct for the drift in oxygen saturation found in previous studies with the ARES™ Unicorder.

Analysis of Respiratory Data from ARES: Data from the monitor will be autoscored and then manually reviewed by a single trained sleep technician at NYU SOM. Data from ARES will be de-identified; only the study ID will be used in monitoring. Apneas will be scored when there is a reduction in airflow to less than 10% of baseline. We have extensive experience using the ARES device and have validated it against NPSG (Nocturnal Polysomnography) in over 300 subjects in multiple research studies.

**SA3. Relate nasal resistance to CPAP adherence in patients with OSA and show that reduction of expiratory pressure using Cflex will improve CPAP adherence. Patients with OSA will be randomized in a double blind cross over design to receive CPAP or CPAPFlex and adherence will be measured as average hours of use over 2 weeks.**

**Protocol for SA3** 1. From the ARES studies, we expect to identify ~500 subjects with OSA. We expect about 10% to refuse to even try CPAP. All others would be recruited to be randomly assigned to CPAP or CPAPFlex as a first treatment, and crossed over to the other after completing the first arm of the protocol.

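### The SAP's primary GEE names no nasal-resistance term, so as stated it cannot test Hypothesis 3b, although randomisation is stratified on resistance

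*SAP*

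**What the plan says.** The SAP (Primary Outcome Measure, Statistical method) gives one primary analysis: GEE models, "with mean hours per night as the dependent variable, will be used to compare the device use of standard CPAP and CPAP flex". It lists no covariate, stratum, subgroup or interaction. The secondary GEE, on AHI, has the same form.

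The protocol gives nasal resistance a central place:

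- Section 1, Hypothesis 3b: CPAPFlex will improve adherence "in subjects with high nasal resistance, but not in those with low nasal resistance".
- Section 1, Hypothesis 3a: "Increased nasal resistance is associated with decreased adherence to CPAP".
- Section 1, Hypothesis 3c: at high resistance, the benefit "will be greatest if it is offered at CPAP initiation rather than as a" rescue treatment.
- Section 2, Background and Significance: larger randomised studies found no adherence difference between the two modes, but "none of these studies have attempted to target therapy to patients based on elevated nasal resistance as we propose to do".
- Procedures for SA3, Randomization and Blinding: allocation is "stratified by site and low" or high resistance, divided at log[Reff] 1.0.
- Section 4.1: the treatments are to be tested according to nasal resistance.

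The design is a two-period crossover. Each patient is randomised to one mode and "crossed over to the other after completing the first arm of the protocol" (Protocol for SA3, item 1).

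**The concern.** Hypothesis 3b is a statement about effect modification. It needs an estimate of CPAPFlex minus CPAP in each resistance stratum and a test of whether the two differ. The stated primary model supplies neither. A treatment main effect suits the general SA3 headline, but it repeats the untargeted comparison from which the Background section sets this trial apart.

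If the SAP is followed as written, the hypothesis that distinguishes the trial goes unanswered. If a resistance analysis is added once the data have been seen, and no other plan document specifies it, the answer to 3b becomes post hoc.

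Two related gaps sit in the same sentence of the SAP. There is no model for 3a. There is also no period or sequence term, although the design is a crossover and 3c predicts that order matters.

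**Working it through.** The visible documents give no sample-size calculation, alpha, SD, effect size or high-resistance share, so there is no planned figure to reproduce. The main argument is algebra. The power figures only illustrate it.

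**Inputs**

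- From the documents (Protocol for SA3, item 1): about 500 patients with OSA are expected, and "We expect about 10% to refuse to even try CPAP". So N = 500 × 0.9 = 450. This is an expectation, not a powered sample size.
- Assumed: 20% lost as a sensitivity case, N = 450 × 0.8 = 360; high-stratum benefit d = 0.5 h; SD of the within-patient difference 2.0 h; high-resistance share p = 0.3, 0.5 or 0.75; two-sided 5% test; normal approximation.

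**1. What the device-only contrast estimates**

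Overall effect = p × (high-stratum effect) + (1 − p) × (low-stratum effect).

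If 3b is exactly true, this is p × d. With p = 0.5:

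- Truth A (0.5 h high, 0 h low): 0.5 × 0.5 + 0.5 × 0 = 0.25 h.
- Truth B (0.25 h in both strata): 0.5 × 0.25 + 0.5 × 0.25 = 0.25 h.

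Both give z = 0.25 × √450 / 2.0 = 2.65, which is 76% power. A larger sample estimates the same 0.25 h more precisely and still does not say which truth produced it.

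**2. What the interaction adds**

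The interaction is 0.5 h under A and 0 h under B. Its standard error is 2.0 × √(1/225 + 1/225) = 0.189 h, so z = 0.5 / 0.189 = 2.65 under A. It is rejected 76% of the time under A and 5% under B.

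**3. Simulation check**

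- N = 450, p = 0.5, SD 2.0 h, 200 runs per case. The device-only GEE averaged 0.39 h in each of three cases: 0.8 h at high resistance only, 0.4 h in both strata, and 0.8 h at low resistance only, the reverse of 3b. It was significant in 98%, 99% and 97.5% of runs. The interaction term averaged +0.80, +0.01 and −0.79 h.
- Two-period crossover with an assumed period effect of −0.2 h, 400 runs. The treatment-only GEE gave 0.250 h under A and 0.251 h under B. With treatment by stratum, period and sequence, the high/low estimates were 0.50/0.00 h under A and 0.27/0.24 h under B. The interaction was rejected in 75% and 4% of runs. The omitted period term did not bias the overall estimate here.

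**4. Power when 3b is exactly true**

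- Overall: z = p·d·√N / SD
- High stratum: z = d·√(Np) / SD
- Interaction: z = d / [SD·√(1/(Np) + 1/(N(1−p)))]

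| N | p | Overall | High stratum | Interaction |
|---|---|---|---|---|
| 450 | 0.3 | 36% | 83% | 68% |
| 450 | 0.5 | 76% | 96% | 76% |
| 450 | 0.75 | 98% | 99.6% | 63% |
| 360 | 0.3 | 30% | 74% | 58% |
| 360 | 0.5 | 66% | 92% | 66% |
| 360 | 0.75 | 94% | 98% | 54% |

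If the SD varies from 1.5 to 2.5 h, interaction power at N = 450 runs from 45% to 94% over these shares. With SD 2.5 h, p = 0.75 and N = 360 it is 38%.

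**5. When the overall contrast is the more powerful one**

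Let r be the low-stratum benefit as a fraction of the high-stratum benefit. The overall z is [p + (1 − p)r]·d·√N / SD. It exceeds the high-stratum z when r > √p / (1 + √p): 35% at p = 0.3, 41% at p = 0.5 and 46% at p = 0.75. For example, p = 0.3 and r = 0.5 give 93% overall against 83% in the high stratum.

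**6. Precision at N = 450**

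95% CI half-widths for high stratum, low stratum and interaction are 0.34, 0.22 and 0.40 h at p = 0.3; 0.26, 0.26 and 0.37 h at p = 0.5; and 0.21, 0.37 and 0.43 h at p = 0.75.

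**The case against.** The strongest reply is redaction. Two blocks are blacked out after protocol section 4.4 and the next heading is section 6. The bibliography ends with a power primer and a biostatistics textbook that no visible text cites. A statistical section may well lie behind the redaction and may specify the test of 3b. This stands as a limit: nothing can be said about the whole plan, and the post hoc risk is conditional. It does not change what the SAP states.

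Second, the SAP may simply be brief. It speaks of models in the plural and lists no covariates at all, so it does not rule out a resistance term. That is true, but a term that is not named is not prespecified.

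Third, the primary outcome matches the SA3 headline, and no visible text makes 3b the primary hypothesis. This also stands. The overall contrast is a legitimate analysis and should be kept. What is missing is any stated analysis for a named hypothesis.

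Fourth, the power figures rest on assumptions and have no fixed direction: the loss nearly vanishes at p = 0.75 and reverses if low-resistance patients benefit enough. Agreed. The conclusion rests on step 1 of the working, which needs no power figure.

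Fifth, the stratum may be less clear-cut than it looks. Rhinomanometry is done seated and lying, before and after decongestion, and the visible text does not say which reading supplies log[Reff]. The allocation table is described only by site. Both are fair points for the fix.

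**Conclusion.** The concern holds, as a statement about the SAP. Its only stated primary analysis compares the two devices. That contrast cannot test Hypothesis 3b at any sample size, because benefit confined to high resistance, uniform benefit and the reverse of 3b can all give the same estimate. This conclusion needs no assumed figures.

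The loss of power is illustrative and depends on the unstated high-resistance share. If 3b is exactly true, with d = 0.5 h, SD 2.0 h and N = 450, overall against high-stratum power ranges from 36% against 83% (p = 0.3) to 98% against 99.6% (p = 0.75). This should be fixed; it does not invalidate the overall comparison.

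**What to change.** Specify the primary GEE with treatment, resistance stratum as randomised (log[Reff] ≤ 1.0 or > 1.0), treatment by stratum, site, period and sequence. Then state:

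- which rhinomanometry reading defines the stratum, and whether allocation blocks were formed within stratum as well as site;
- that CPAPFlex minus CPAP is reported with a 95% CI in each stratum;
- that the interaction test addresses the low-resistance half of 3b, and that a non-significant low-stratum result will not be read as no benefit;
- that the overall contrast is kept for the SA3 headline;
- which contrast is primary and, if the overall and high-stratum contrasts are both confirmatory, their order or alpha split;
- for 3a, a regression of adherence in the standard-CPAP period on continuous log[Reff], adjusted for site and period.

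Hypothesis 3c needs its own contrast, which this change does not supply.

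The cost is SAP wording. Resistance is measured before randomisation, so no new data are needed. The downside is the limited interaction power shown above, which is a reason to lead with the stratum estimates and their intervals. If the redacted protocol text already contains this analysis, the SAP need only restate it or refer to it.
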